3.3.9. Combining Data Across Panels

When data are combined across panels to create composite endpoints, like complete response, information will be combined in the following manner:

1. Data will be merged by visit for each subject.
2. Unscheduled and early termination data will be windowed according to the visit windows below. Additionally, data from visits where pathology, cytology, and cystoscopy are unexpected (i.e., Maintenance Month 4) will be windowed using the table below.
3. Data within a given visit window will be collapsed to the worst-case result. For example, if a subject has two central pathology assessments for a given visit one with 'CIS' and the other with 'No Tumor', the analysis result for the collapsed visit will be considered as 'CIS'.
4. The date corresponding to the collapsed visit will be the earliest observed date for the visit.

Analysis Visit	Study Days
Screening	-8 < Study Day < 1
Week 1	1 <= Study Day <= 49
Post Induction Phase	49 < Study Day <= 137
Maintenance Month 3	137 < Study Day <= 227
Maintenance Month 6	227 < Study Day <= 318
Maintenance Month 9	318 < Study Day <= 409
Maintenance Month 12	409 < Study Day <= 500
Maintenance Month 15	500 < Study Day <= 591
Maintenance Month 18	591 < Study Day <= 682

Maintenance Month 21	682 < Study Day <= 773
Long-term Follow up Month 3	773 < Study Day <= 864
Long-term Follow up Month 6	864 < Study Day <= 955
Long-term Follow up Month 9	955 < Study Day <= 1046
Long-term Follow up Month 12	1046 < Study Day <= 1137
Long-term Follow up Month 15	1137 < Study Day <= 1228
Long-term Follow up Month 18	1228 < Study Day <= 1319
Long-term Follow up Month 21	1319 < Study Day <= 1410
Long-term Follow up Month 24	1410 < Study Day <= 1501

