### 10.4 Post-Induction Phase Evaluation

Subjects will be evaluated for disease status at the end of the Induction Phase. Urine cytology is obtained in week 12 as described above. Starting in week 13 (or as soon as possible after week 12) subjects will undergo cystoscopy and directed biopsies/TURBT of all lesions suspicious for disease. Subjects are eligible to receive Maintenance Phase treatment if they do not have a protocol defined treatment failure (see [Section 14.2](#)) or other criteria for study drug discontinuation (see [Section 14.3](#)) and are tolerating treatment.

See [Section 14.4](#) for criteria to continue treatment.

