Subjects' disease status will be evaluated based on cystoscopy (and biopsies if indicated) and urine cytology at the end the Induction Phase (week 13) and every 13 weeks during the Maintenance Phase (i.e., Week 26, Week 39, Week 52, Week 65, Week 78, Week 91, Week 104) regardless of dosing interruptions or delays. For subjects who discontinue treatment for reasons other than disease progression ([Section 14.2](#)), cystectomy or death, the every 13-week disease evaluation should continue for the determination of secondary endpoints e.g., event-free survival, progression-free survival. Every effort should be made to stay on this evaluation schedule, however, a window of one week before and up to 2 weeks after these time points is permitted (e.g., the Week 26 cystoscopy and urine for cytology may be performed from week 25 to week 28, but as close to Week 26 as possible). The complete evaluation to determine disease status may require a repeat cytology and repeat cystoscopy with biopsies (See [Table 7](#)) and should be completed as soon as possible following the every 13-week timepoint. On cystoscopy, any areas suspicious for disease must be biopsied. In situations where there are no suspicious lesions on cystoscopy but a positive or suspicious result on urine cytology, random bladder biopsies will be obtained from the locations of disease identified at Screening (i.e., by screening biopsies and the screening bladder mapping) and from other areas of the bladder so that all the following areas of the bladder have been biopsied: the dome, the posterior wall, the left and right lateral walls, the trigone and the bladder neck, and in males, the prostatic urethra. A second urine cytology will also be required at the time of evaluation if the result of the first urine cytology is suspicious for urothelial carcinoma. The use of other diagnostic evaluations (e.g. urine FISH) or the performance of additional urine cytology, cystoscopies, and/or biopsies not mandated by the protocol may be performed when clinically indicated per the investigator's clinical judgment or standard of care. Results of urine FISH will not be considered in the response evaluation but may be used by the investigator to guide additional (non-protocol mandated) evaluations.

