Subjects with CIS (Cohort 1 or Cohort 2) will be considered to have a complete response if at the time of any disease status evaluation (per protocol every 13 weeks or any unscheduled evaluation) there is no evidence of high-grade disease (CIS, high-grade Ta or any grade T1 disease) or disease progression (e.g., to muscle invasive disease). Subjects whose initial diagnosis was CIS who are found to have low-grade Ta disease at the time of an evaluation must have the low-grade disease resected by TURBT. Low-grade Ta disease is not considered a treatment failure in these subjects and they may remain on study treatment following TURBT.

Date of Complete Response or Treatment Failure

Given that the cystoscopy, biopsy, and cytology assessments may be conducted on different dates, the date of complete response or treatment failure will be defined as the earliest assessment date of these assessments.

Duration of Response

Duration of Response will be analyzed for subjects with CIS with or without papillary disease (Cohort 1 + Cohort 2) who achieve complete response using a Kaplan-Meier (KM) product-limit method. It is defined as the number of days from the date of first occurrence of complete response to the date of documented treatment failure or death, whichever occurs first. Subjects who do not experience treatment failure or death will be censored at their last assessment of response.

Event

For the purposes of defining Event-Free Survival, an event is defined as treatment failure or death on or prior to treatment discontinuation. Because disease assessments are not recorded after treatment discontinuation, a death after treatment discontinuation will not be counted as an event so as not to artificially inflate EFS. Presence of upper or lower urinary tract urothelial carcinoma and having a cystectomy are not treated as events for analysis but do trigger special data handling in the event-free survival analysis.

Event-Free Survival

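### SAP 3.3.9 merges a later, separate positive result into an already completed negative evaluation, which misdates failures and removes the shortest responders from duration of response

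*SAP*

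**What the plan says.** SAP 3.3.9 governs how pathology, cytology and cystoscopy are put together: "When data are combined across panels to create composite endpoints, like complete response". Three of its steps matter here.

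- "Unscheduled and early termination data will be windowed according to the visit windows below".
- "Data within a given visit window will be collapsed to the worst-case result". The SAP's own illustration turns one CIS reading and one tumour-free reading for the same visit into CIS.
- "The date corresponding to the collapsed visit will be the earliest observed date for the visit".

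The Post Induction window, which supplies the 3-month response, is "49 < Study Day <= 137". The next window (Maintenance Month 3, holding the Week 26 evaluation) ends on Day 227.

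The scheduled 3-month evaluation is narrower. Protocol 10.3.5 collects cytology in Week 12, and Protocol 10.4 adds: "Starting in week 13 (or as soon as possible after week 12) subjects will undergo cystoscopy". Outside the schedule, Protocol 14 provides that "additional urine cytology, cystoscopies, and/or biopsies not mandated by the protocol may be performed when clinically indicated", and it has those samples centrally read as well.

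Under SAP 5.2.1, a failing central pathology or cytology result makes the subject a failure at that visit and at every later visit. SAP 3.3.7 defines response differently. A CIS subject responds "if at the time of any disease status evaluation (per protocol every 13 weeks or any unscheduled evaluation) there is no evidence of high-grade disease", and duration runs from the first such response to documented failure or death. The same section dates a response or failure at the earliest of the component assessments.

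**The concern.** Worst-case merging makes sense within one evaluation. Protocol Table 6 may require biopsies and a second cytology before disease status is settled, and those results belong together. SAP 3.3.9, however, merges by calendar window and not by evaluation. A new sample taken weeks after a negative evaluation was closed is treated as part of it, and the failure is given a date on which the subject had no evidence of disease.

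Three results are affected: the 3-month complete response rate (a primary endpoint in SAP section 2), duration of response (listed beside it), and event-free survival, which uses the same failure dates. Neither sensitivity analysis in SAP 5.2.3 tests the merge. One concerns missing central readings after an abnormal cystoscopy, and the other counts low-grade Ta as failure. SAP 3.3.8 does prefer the scheduled value over an unscheduled one, but it covers by-visit displays and does not override 3.3.9 for response.

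**Working it through.** **Plan figure.** The documents give no figure for the effect of this rule. The nearest is the precision table in SAP 3.1. The Clopper-Pearson lower limit, the 2.5% quantile of Beta(x, n − x + 1) with x = 0.30n, first reaches 0.220, 0.210 and 0.200 at n = 121, 95 and 76, which matches the table.

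**Window arithmetic** (SAP 3.3.8 and 3.3.9; Protocol 10.4 and 10.5)

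- Week 12 starts on Day 78. Week 13 is Days 85-91. The Post Induction window is Days 50-137.
- Time left in the window after a Week 13 cystoscopy: 137 − 91 = 46 to 137 − 85 = 52 days.
- Largest backdating to the Week 12 cytology: 137 − 78 = 59 days.
- Week 26 starts on Day 176, and the earliest permitted visit (start of Week 25) is Day 169. The window ends on Day 227. Backdating is up to 227 − 176 = 51 days, or 227 − 169 = 58 days from the earliest permitted visit.

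**One subject followed through.** Take negative cytology on Day 78, negative cystoscopy on Day 88, and CIS on an unscheduled biopsy on Day 130.

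- By SAP 3.3.7: response at 3 months, failure on Day 130, duration 130 − 78 = 52 days.
- By SAP 3.3.9: failure at 3 months dated Day 78, which is 88 − 78 = 10 days before the negative cystoscopy. SAP 5.2.1 carries the failure forward, so the subject is never a responder and never enters the duration analysis.
- The same biopsy on Day 138 falls in the next window and leaves the 3-month response intact.

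**Size for the response rate.** Each such subject costs 1/n, which is 1/77 = 1.3 points at the Cohort 1 minimum and less once Cohort 2 is added. The number of such subjects is not given, so a range is assumed:

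- Expected loss = R × q × d.
- R = 23 scheduled responders of 77 (29.9%, near the 30% planning rate).
- q = share of them given an extra biopsy or cytology by Day 137 (assumed 10% to 100%).
- d = 1 − exp(−46h), the chance of relapse in 46 days. The Phase 2 results in Protocol section 7 serve only to set a range for h. Median 408 days gives d = 7.5%; median 274 days gives 11.0%; 7 of 20 responders still disease-free after about 274 further days gives 16.2%. The rows below use 7.5% and 16%.

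| q | Subjects lost | Response rate, from 29.9% |
|---|---|---|
| 10% | 0.2-0.4 | 29.7-29.4% |
| 50% | 0.9-1.8 | 28.8-27.5% |
| 100% | 1.7-3.7 | 27.6-25.1% |

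At the planning boundary one subject can show: 24 of 77 has an exact lower limit of 0.2109, and 23 of 77 has 0.1997. The SAP uses 0.20 for planning and does not state it as a success threshold.

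**Size for duration of response.** Removing early relapsers raises the modelled share with duration over 365 days, exp(−365h)/(1 − qd). From q = 0 to q = 100% it goes from 54% to 58%, from 40% to 45%, and from 25% to 29% for the three values of h. Backdating works the other way. With response dated Day 78 and a negative Week 26 evaluation on Day 176, a relapse found on Day 227 gives 176 − 78 = 98 days instead of 227 − 78 = 149.

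**The case against.** The strongest defence is that the rule is prespecified, needs no judgement, and is conservative for a single-arm response rate. The evaluation legitimately spans several days and repeat tests, contiguous windows must end somewhere, and the definitions of both response and failure expressly include unscheduled evaluations. A different rule would require someone who knows the results to decide whether a positive is separate, and each such decision would add a responder.

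Much of this stands. More sampling can only lower the response rate under the present rule, and the day shifts above are near-maximum because they assume a positive at the very end of a window. But counting unscheduled findings as failures does not require erasing an earlier completed response. Nor is the rule conservative for duration, since it removes the shortest responders. The judgement problem can be met with an objective closing rule.

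Two stronger readings are tempting. A reader might infer that 3-month response depends on how many extra cystoscopies a site performs. SAP 5.2.1 does not support that: a cystoscopy alone cannot produce failure, and a centrally read biopsy or cytology is needed. A reader might also infer that results differ by site. The protocol leaves extra tests to clinical indication, but nothing in the documents shows that sites vary in their use.

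**Conclusion.** The point holds as a defect in the stated rule. It assigns failure dates that precede documented negative findings, and it conflicts with SAP 3.3.7 on who is a responder.

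For the response rate the effect is downward only and probably small: at most 1.3 points per affected subject, and under half a subject expected in 77 if 10% of scheduled responders are re-sampled. The larger losses require half or all of them to be re-sampled by Day 137. The range rests on assumed q, a constant relapse hazard borrowed from Phase 2, and n = 77, whereas the SAP's primary population is Cohorts 1+2.

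For duration of response, removal of early relapsers lengthens the curve and backdating of up to about 51-58 days shortens it. A reader might conclude that duration is overstated, or that it is understated. The documents support neither, because the number and timing of unscheduled positives are unknown. Event-free survival dates move earlier.

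**What to change.** In SAP 3.3.9, and in the date rule of SAP 3.3.7:

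- Apply the worst-case and earliest-date rules only to the scheduled cytology and cystoscopy and to the biopsies and repeat cytology they trigger under Protocol Table 6.
- Close an evaluation by an objective rule: all required components are negative and no Table 6 test is outstanding. Score that visit as it stands.
- Treat a later central positive as treatment failure on its own assessment date, carried to the next and all later visits.
- Report the present window-wide collapse as a conservative sensitivity analysis for the response rate.

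The cost is SAP wording and a change to the derivation program, using dates already collected. Repeat samples must be linked to their parent evaluation, and the linking rule should be written down before it is applied. The change does not make duration of response or event-free survival independent of surveillance: a relapse found at an unscheduled visit will still be dated earlier than one found at the next scheduled visit.

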  - For subjects with T1 disease: the base of the tumor bed must be adequately biopsied so that the sample includes muscle from the base of the lesion(s) in order to demonstrate an absence of muscle invasion. All subjects with T1 disease must undergo a second resection (i.e., restaging TURBT) approximately 2 - 6 weeks after the initial TURBT. Postoperative intravesical chemotherapy (e.g., mitomycin) is acceptable per investigator discretion but cannot be given within 2 weeks of the first dose of Vicinium. For subjects with T1 disease who undergo a restaging TURBT, Vicinium treatment must start within 6 weeks of the restaging TURBT or the last biopsy/TURBT that determines eligibility.
  - **NOTE: Subjects should not receive Vicinium treatment within 2 weeks of any biopsy/TURBT in order to permit bladder healing**

- Additional resections or restaging TURBTs not required by this protocol may also be done at Investigator discretion e.g., for high-grade Ta disease, if this is within acceptable practice standards
- Subjects with T1 disease must also have radiological examination (i.e., CT urogram or MRI urogram) of the abdomen and pelvis to rule out more advanced disease. If intravenous contrast is contraindicated, retrograde ureteropyelography, or CT or MRI without intravenous contrast may be performed.
- Prostatic urethral biopsy (males subjects) is recommended particularly for subjects at higher risk for prostatic urethral involvement per investigator discretion. It is not required.
- Upper tract radiological imaging, i.e., CT urogram or MRI urogram of the abdomen and pelvis, is required if this has not performed within 13 weeks before start of dosing. If intravenous contrast is contraindicated, retrograde ureteropyelography, or CT or MRI without intravenous contrast may be performed. (Note: imaging during screening is a requirement for all subjects with T1 disease as noted above)
- EpCAM determination by immunohistochemistry will be performed on all positive biopsies (baseline and any post-baseline positive biopsies during the study), but confirmation of this is not required prior to enrollment into the trial or the start of study drug administration. Additional unstained slides should be submitted for all positive biopsies for biomarker evaluation ([Section 16.7](#))
- Demographics ([Section 16.1](#))
- Review of medical history, including relevant past medical conditions including other cancers and surgical procedures ([Section 16.1](#))

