 White-light cystoscopy. Any subject who undergoes fluorescence cystoscopy for bladder biopsy/TURBT during the screening period must continue having this modality for all subsequent biopsies (however, white-light cystoscopy will suffice for all assessments if a biopsy is not required ([Section 14](#))).

 Directed biopsies of all areas suspicious for disease. Random biopsies are required if cystoscopy is negative and urine cytology is positive or there are two suspicious cytology results ([Section 14](#))

 CT urogram or MRI urogram. If intravenous contrast is contraindicated, retrograde ureteropyelography, or CT or MRI without intravenous contrast may be performed. Required during Screening for all subjects with T1 disease. Required for all other subjects if not previously performed within 13 weeks before the start of dosing.

 Single tracing only at Screening unless QTc is prolonged ([Section 16.4](#)); thereafter, triplicate ECGs are to be performed.

 Update medication history.

 Performed every 4 weeks (i.e., week 4, week 8, week 12, etc.) while on treatment in females of childbearing potential only.

 Cytology sample pre-dose on Day 1. Note: Chemistry, hematology (CBC and differential), urinalysis and physical examination need to be performed pre-dose Day 1 only if not performed in the Baseline Period ( $\leq 7$  days before the first dose of study medication).

 Evaluation performed pre-dose and post-dose prior to leaving the clinic.

 Evaluation performed pre-dose. Concomitant medications required post-dose only if additional medications (not including Vicinium) were administered during or after the start of the instillation.

 Weeks 2-5: Chemistry and hematology (CBC and differential) performed once weekly ([Section 10.3.2](#)). Week 4: Targeted physical examination. Week 6: Urinalysis performed pre-dose at the second dose of the week; Hematology (CBC and differential) and chemistry ([Section 10.3.3](#)). Weeks 7-11: Chemistry and hematology (CBC and differential) performed once weekly ([Section 10.3.4](#)). Week 8: Targeted physical examination. Week 12: Urinalysis performed pre-dose. Hematology (CBC and differential), chemistry([Section 10.3.5](#)). Targeted physical examination, and triplicate ECG performed post-dose prior to leaving the clinic.

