3.3.7. Definitions and Terminology

Adverse Event

An adverse event (AE) is defined as any unfavorable and unintended sign (including an abnormal laboratory finding), symptom or disease temporally associated with the use of a medical treatment or procedure regardless of whether it is considered related to the medical treatment or procedure (attribution of unrelated, unlikely, possible, probable, or definite).

Any medical condition that is present at the time the subject is screened, but does not deteriorate, should not be reported as an AE. However, if it deteriorates at any time during the study it should be recorded as an AE. Hospitalization for elective treatment of a preexisting condition that did not worsen from baseline is not considered an AE or serious AE (SAE).

The descriptions and grading scales found in the revised National Cancer Institute Common Terminology Criteria for Adverse Events (NCI-CTCAE) version 4.03 will be utilized for AE reporting.

Serious Adverse Event

A serious adverse event is any AE that is fatal, life-threatening, requires or prolongs hospital stay, results in persistent or significant disability or incapacity, results in a congenital anomaly or birth defect, or is an otherwise important medical event.

Treatment-emergent AE

Treatment-emergent AEs (TEAEs) are all AEs occurring on or after the date of first dose of study drug through 30 days post the last dose of study drug.

Baseline Value

For purposes of analysis, the baseline value is defined as the last value obtained prior to the first dose of Vicinium.

Study Drug

For the purposes of this study, the term study drug refers to Vicinium.

Day 1 (Baseline)

Day 1 is the day that the first dose of Vicinium is received.

Age

The age of a subject is defined as (Date of Informed Consent – Date of Birth + 1)/365.25.

Study Day

Study Day is defined relative to Baseline (Day 1). Thus, the study day of an event is calculated as:

$$\text{Study Day} = \text{event date} - \text{date of Day 1} + 1.$$

Change from Baseline

Change from baseline for a given endpoint is defined as the Study Day X value minus the Baseline Value.

Cohort 1 Subjects

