3.3.8. By-Study Visit Displays

When data are collected serially over time, individual data presentations may include by-visit displays. Visits will be presented according to the nominal visit as obtained from the CRF or laboratory. If assessments are collected multiple times within a given visit, the value from the scheduled visit will be chosen over the value from the unscheduled visit. If there are two or more assessments with the same nominal visit label, the value closest to the nominal visit will be summarized. If two assessments have the exact same distance from the nominal visit by date and time, if applicable, then the last visit will be chosen for summarization. Unscheduled, End of Treatment, and Post Treatment Follow-Up Visits will be windowed according to visit date so that these data are appropriately analyzed. The following visit windows will be applied according to the following table:

Analysis Visit	Study Days	Target Study Day for Visit
Baseline	-8 < Study Day <= 1	
Week 1	1 < Study Day <= 7	1
Week 2	7 < Study Day <= 14	8
Week 3	14 < Study Day <= 21	15
Week 4	21 < Study Day <= 28	22
Week 5	28 < Study Day <= 35	29
Week 6	35 < Study Day <= 42	36
Week 7	42 < Study Day <= 49	43
Week 8	49 < Study Day <= 56	50
Week 9	56 < Study Day <= 63	57
Week 10	63 < Study Day <= 70	64
Week 11	70 < Study Day <= 77	71
Week 12	77 < Study Day <= 84	78
Week 13	84 < Study Day <= 91	85

Analysis Visit	Study Days	Target Study Day for Visit
Maintenance Month 1	91 < Study Day <= 121	115
Maintenance Month 2	121 < Study Day <= 152	146
Maintenance Month 3	152 < Study Day <= 182	176
Maintenance Month 4	182 < Study Day <= 212	206
Maintenance Month 5	212 < Study Day <= 243	237
Maintenance Month 6	243 < Study Day <= 273	267
Maintenance Month 7	273 < Study Day <= 303	297
Maintenance Month 8	303 < Study Day <= 334	328
Maintenance Month 9	334 < Study Day <= 364	358
Maintenance Month 10	364 < Study Day <= 394	388
Maintenance Month 11	394 < Study Day <= 425	419
Maintenance Month 12	425 < Study Day <= 455	449
Maintenance Month 13	455 < Study Day <= 485	479
Maintenance Month 14	485 < Study Day <= 516	510
Maintenance Month 15	516 < Study Day <= 546	540
Maintenance Month 16	546 < Study Day <= 576	570
Maintenance Month 17	576 < Study Day <= 607	601
Maintenance Month 18	607 < Study Day <= 637	631
Maintenance Month 19	637 < Study Day <= 667	661
Maintenance Month 20	667 < Study Day <= 698	692
Maintenance Month 21	698 < Study Day <= 773	722

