5.2. EFFICACY ANALYSIS

5.2.1. Primary Efficacy Endpoint

The primary outcome measure is the complete response rate in subjects with refractory /relapsed CIS or CIS plus papillary disease (i.e., cohorts 1 and 2) following the initiation of Vicinium therapy.

Patients who discontinue or die before Month 3 will be included in the denominator of the primary analysis.

For the primary efficacy endpoint analysis, the following conventions will be utilized in determining treatment failure or complete response at a given visit.

1. Subjects that have centrally read pathology findings ('CIS', 'any-grade T1', 'high-grade Ta') or centrally read cytology results ('High Grade Urothelial Carcinoma') that indicate treatment failure for a given visit will be considered to have treatment failure.
2. Subjects who met a treatment failure criterion at a previous visit are treatment failures at all subsequent visits.
3. Subjects who have discontinued the study on or prior to the visit and have missing data that would be necessary to generate response are considered non-CRs.
4. Subjects who do not meet criterion 1-3 are complete responders.

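### SAP 3.3.9 puts the Day 1 pre-dose urine cytology in a composite 'Week 1' response visit, contradicting the SAP's own definition of baseline

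*SAP*

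**What the plan says.** **Timing of the sample.** Protocol Table 3, footnote 8, reads "Cytology sample pre-dose on Day 1". Protocol 10.3.1 lists the same sample under the first dose of Week 1, and the schedule in SAP 1.2 shows it in the Week 1 column.

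**Baseline.** SAP 3.3.7 states that "the baseline value is defined as the last value obtained prior to the first dose of Vicinium". It also counts the first-dose date as Study Day 1. In SAP 3.3.8 the Baseline row reads, after a leading minus sign, "8 < Study Day <= 1", so Day 1 belongs to Baseline.

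**Composite response.** SAP 3.3.9 merges scheduled data by visit. It uses date windows for unscheduled and early-termination data, and for visits where these tests are not expected. All results in a visit are then collapsed to the worst one and given the earliest date. Its Screening row reads, after a leading minus sign, "8 < Study Day < 1". Its Week 1 row reads "1 <= Study Day <= 49".

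**Scoring.** Under SAP 5.2.1, rule 1, a high-grade central cytology at a visit is a treatment failure. Rule 2 adds: "Subjects who met a treatment failure criterion at a previous visit are treatment failures at all subsequent visits".

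**The concern.** The same pre-dose sample is baseline in two places in the SAP and part of an on-treatment visit in the section that builds the primary endpoint. A pre-dose cytology describes the disease the subject brought into the trial and carries no information about the drug. If it is scored with on-treatment results, two things can go wrong:

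- A subject with positive entry cytology could be counted as a failure at every later visit, even when the end-of-induction evaluation is clear.
- A real failure found at an unscheduled evaluation during the first seven weeks would take the date of the pre-dose sample.

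The first would lower the complete response rate, so it works against the drug. The second concerns dates and arises even when entry cytology is negative. Both bear on the primary-endpoint derivation of an open-label, single-arm trial, where the programming should follow from the text without interpretation.

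**Working it through.** The plan states no figure that this point disputes. The check applies the SAP's rules to the sample in order.

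**1. Study Day of the sample.** By the SAP 3.3.7 formula, Study Day = (Day 1 date − Day 1 date) + 1 = 1.

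**2. Window tests for Study Day d.**

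| d | 3.3.8 Baseline (−8 < d ≤ 1) | 3.3.9 Screening (−8 < d < 1) | 3.3.9 Week 1 (1 ≤ d ≤ 49) |
|---|---|---|---|
| −1 | in | in | out |
| 1 | in | **out** | **in** |
| 2 | out | out | in |
| 49 | out | out | in |
| 50 | out | out | out |

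Day 1 is the only day in this list that the two tables treat differently. The 3.3.8 windows are themselves introduced for unscheduled, end-of-treatment and follow-up visits. The firmest statement that the sample is baseline is therefore the definition in 3.3.7, which 3.3.8 agrees with.

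**3. How data reach Week 1.**

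- The Day 1 cytology is scheduled, so it enters by visit label. Both schedules label it Week 1. I assume that the case report form uses the same label.
- Unscheduled evaluations on Days 2 to 49 enter by date window.

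The two kinds of data meet in one analysis visit.

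**4. Collapsing.** Worst result and earliest date, applied to the pooled visit:

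| Day 1 pre-dose cytology | Unscheduled evaluation, Days 2–49 | Collapsed Week 1 result | Collapsed date |
|---|---|---|---|
| Positive | None | Positive | Day 1 |
| Positive | Clear | Positive | Day 1 |
| Negative | Failure on day d | Failure | Day 1 |

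In the last row the date is too early by d − 1 days. That is 2 − 1 = 1 day at the least and 49 − 1 = 48 days at the most. A failure found on Day 40 would be dated 39 days early.

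**5. Scoring.** Rule 1 of SAP 5.2.1 works visit by visit, and rule 2 carries failure forward. Neither names the first visit to which it applies, and neither excludes a pre-dose result. Read literally, the first two rows of the second table are permanent failures.

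**6. Size.** Let f be the share of CIS subjects with positive entry cytology. Under the literal reading the complete response rate could not exceed 1 − f at any visit. The documents do not give f, nor how entry cytology relates to response, so no response rate follows.

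**The case against.** The strongest reply is that the endpoint definitions already keep a pre-dose sample out, and much of it stands:

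- SAP 3.3.7 describes treatment failure as evidence that the drug cannot achieve or maintain a response. Its histology bullet is tied to 13-weekly or unscheduled evaluations, and its cytology bullet to loss of an existing response.
- The complete response definition carries the same timing.
- Protocol Section 10 has the first disease evaluation only once induction is finished, and SAP Section 2 sets complete response at 3 months and later.
- Screening is also a row in the 3.3.9 table. If the rules were applied to every row, all CIS subjects would fail on their qualifying pathology, which cannot be meant.

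This shows the intent, but it does not repair the text. Excluding Screening is simple because that row is wholly pre-dose. Week 1 is mixed: dropping it would discard genuine unscheduled failures on Days 2 to 49, and keeping it pools them with the baseline sample.

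The reply is also right that the date windows formally cover unscheduled, early-termination and unexpected-visit data. The Day 1 cytology reaches Week 1 by its label and not through the quoted window.

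A reader might infer more from these passages. The documents do not support the following:

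- **Duration of response starting at Week 1.** The response definition requires a disease status evaluation, no cystoscopy is scheduled in Week 1, and the planned landmark plots start from response at Months 3, 6, 9 and 12.
- **Event-free survival certainly carrying Day 1 events.** The SAP's event table uses the date of treatment failure. Whether the collapsed date feeds into it depends on programming that is not described.
- **Qualifying biopsies lost from the short Screening window.** They are scheduled screening procedures and are merged by label.
- **Day 1 as the only entry cytology.** The protocol synopsis and Section 14 also mention urine cytology at Screening.

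**Conclusion.** Wrong as written: the 3.3.9 window rule contradicts the SAP's own definition of baseline, and 5.2.1 has no sentence that resolves the conflict. What holds without any assumption about entry cytology is the back-dating by 1 to 48 days of a failure found at an unscheduled evaluation on Days 2 to 49, when the 3.3.9 collapsing steps are followed. It rests only on the Day 1 sample being labelled Week 1, as in both schedules.

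A reader might conclude that the primary complete response rate will be wrong by a stated amount. The documents do not support that. The permanent-failure outcome needs a literal reading that other parts of the plan speak against, the programming actually used is not described, and the share with positive entry cytology is not given. This is a contradiction to correct in the primary-endpoint derivation, not a demonstrated corruption of the result.

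**What to change.** In SAP 3.3.9, assign every pre-dose sample, including the Day 1 pre-dose cytology, to Screening/Baseline. Start the first post-baseline window after the first dose, on Day 2, so that it agrees with 3.3.7 and 3.3.8.

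In SAP 5.2.1, add one sentence: rules 1 to 4 apply only to post-dose disease evaluations, and the Day 1 pre-dose cytology serves as baseline only.

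The cost is one window boundary, one sentence and the matching change in the program. It needs no new data and no protocol amendment.
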